## **7. Consent Process**

Approval for medical treatment is obtained by first briefly explaining the background, objectives, and benefits of the research. The informed consent must be fully explained by the investigator or member of the study staff including the study aims, methods, benefits, and risks, and signed by the subject before enrollment into the study. Potential subjects will be informed that study participation is voluntary and that they may withdraw at any time. The subjects will be told that choosing against participation will not affect the care received for treatment. The subjects will be informed that they will be authorized access by investigational staff to confidential medical records. The subjects will be given sufficient time to read the consent and ask any questions. Research participants who are willing to take part in this study then sign an informed consent. Patients who are willing to participate in the study will receive compensation.

## **8. Compensation**

The participants will accept the transportation fee of Rp100.000,00.

## **9. Reasons for Withdrawal or Termination**

A subject may be discontinued from the study at any time if the subject or the investigator feels that it is not in the subject's best interest to continue. The following is a list of possible reasons the subjects will be **dropped out** from the study:

1. Participants withdraw their informed consent and refuse to participate in the study.
2. Any contraindications for 6 Minute Walking Test according to the guidelines of the American Thoracic Society (ATS).
3. Participants who died before the sixth-month follow-up.

All subjects are free to withdraw from participation at any time, for any reason, specified or unspecified, and without prejudice. Reasonable attempts will be made by the investigator to provide a reason for subject withdrawals. The reason for the subject's withdrawal from the study will be specified in the subject's source documents and the Case Report Form (CRF). If a subject is withdrawn from treatment due to an adverse event, the subject will be followed and treated by the investigator until the adverse event has resolved or stabilized.

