## 5.4. Data Collection

Data on age, sex, height, weight, body mass index, income, education, comorbidities, smoking, alcohol consumption, documented SARS-CoV-2 vaccination

status (including the amount, type, and when the vaccine was received), detailed history of laboratory-confirmed SARS-CoV-2 infection, Long COVID symptoms, severity, and duration are collected through online screening questionnaire.

Data on quality of life (QoL) are collected through St George's Respiratory Questionnaire (SGRQ) and Short Form (SF)-36 Health Survey self-assessment questionnaire at baseline, 3 and 6 months after enrollment. SGRQ addresses QoL in the domains of symptoms, activity, and impacts within the last 4 weeks; and the SF-36 Health Survey questionnaire addresses QoL in the domains of vitality, physical functioning, bodily pain, general health perceptions, physical and emotional and social role functioning.

Data on functional exercise capacity is measured using the Six-Minute Walking Test (6MWT) at baseline, 3 and 6 months after enrollment. The 6MWT is performed according to the guidelines of the American Thoracic Society (ATS). During the 6MWT, such data are collected: Blood pressure, oxygen saturation (SpO2), heart rate, dyspnea, and overall fatigue score using the Modified Borg scale before and after the test, and also one-time measurement (total distance walked in 6 minutes, symptoms at the end of exercise).

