## **6. Potential Benefits and Risks**

The 6MWT is a safe test with rare complications. It is a practical, simple test that requires, in ideal circumstances, a 100-foot hallway, no exercise equipment, and no advanced training for technicians. Walking is a daily activity for all but severely

impaired patients and so can be used by most patients in a practice. Patient involvement is based on voluntary participation, is self-directed, and is easily terminated in the event of a complication.

Safety considerations when administering the 6MWT include both technical and clinical aspects. Technical aspects for safety include proper training and knowledge for the person administering the test, adequate facility provision, and emergency provisions. Clinical aspects of safety considerations for the 6MWT include knowledge of absolute and relative contraindications and conditions requiring immediate cessation of the 6MWT. Study documentation of adverse effects reveals oxygen desaturation as the most common adverse effect, with desaturation to less than or equal to 80% in approximately 5% of testing, and patient symptoms prematurely terminating the test in 1% of testing. The absolute contraindications are unstable angina and/or myocardial infarction in the past 30 days. The relative contraindications are resting heart rate above 120 bpm, systolic blood pressure over 180 mmHg, and diastolic blood pressure above 100 mmHg. The reasons for cessation according to the ATS guideline are sudden chest pain, intolerable dyspnoea, leg cramps, staggering, diaphoresis, and pale or ashen appearance.

We take extra effort during the study period to maximize patient safety. Fulfilling this goal, the study staff employs stringent procedures to reduce the risk of adverse events during the study period.

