## **10. Handling of Participant Withdrawals or Termination**

Although subjects may withdraw from the study at any time and for any reason, (or may be withdrawn at the investigator's discretion), subject withdrawal should be avoided as much as reasonably possible. In any case, appropriate follow-up for withdrawals or termination. Subjects who are discontinued are not to be replaced. For subjects considered discontinued, the CRF must be completed up to the last visit performed.

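### A contraindication to the walk test (a secondary measure) removes the subject from the whole study, so later primary quality-of-life data that could still be collected are lost

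*Combined protocol and SAP*

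**What the plan says.** Protocol Section 9 opens its list with "The following is a list of possible reasons the subjects will be", and the sentence ends by naming removal from the study as a whole. Item 2 is "Any contraindications for 6 Minute Walking Test according to the guidelines of the American Thoracic Society (ATS)". Item 3 is "Participants who died before the sixth-month follow-up".

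Section 10 adds: "For subjects considered discontinued, the CRF must be completed up to the last visit performed". Discontinued subjects are not replaced.

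Section 5.4 collects quality of life by SGRQ and "Short Form (SF)-36 Health Survey self-assessment questionnaire at baseline, 3 and 6 months after enrollment". The 6MWT is done at the same three time points.

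Section 2.1 makes quality of life a primary objective. Section 2.2 makes functional exercise capacity, which the 6MWT measures, a secondary one.

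Section 6 separates two kinds of contraindication. Its first statement reads "The absolute contraindications are unstable angina and/or myocardial infarction in the past 30 days". A second statement then covers milder findings at rest: "The relative contraindications are resting heart rate above 120 bpm, systolic blood pressure over 180 mmHg, and diastolic blood pressure above 100 mmHg".

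**The concern.** The drop-out rule is wider than its reason. A contraindication is a reason not to walk. It is no obstacle to filling in SGRQ or SF-36. As written, a subject in whom one is found after enrolment can leave the study and lose all later quality-of-life assessments.

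The conditions in Section 6 are cardiovascular, and Section 1 counts cardiovascular disorders among the complications of COVID-19. Subjects lost this way may therefore differ in health from those who stay. If so, the 3- and 6-month description of quality of life could look better than it is. If the loss also differs by vaccination group, the vaccine comparison could be distorted. Assessments that were never made cannot be recovered at analysis.

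**Working it through.** **1. Does the rule act after enrolment?** Section 5.2 already excludes subjects with a 6MWT contraindication at entry. Item 2 of Section 9 therefore has a function only for contraindications found later.

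**2. Does anything restore the questionnaires?** Three places could.
- Section 9 follows subjects withdrawn for an adverse event until that event resolves or stabilises. It does not mention SGRQ or SF-36.
- Section 10 has an incomplete sentence on appropriate follow-up that names no data to collect.
- The readable SAP (Sections 3.1 to 3.2.2) gives descriptive statistics and chi-square or Fisher tests, with no analysis set, missing-data method or handling of deaths. The figure under SAP 3.2 is not available.

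None restores them.

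**3. Which contraindications count?** Item 2 of Section 9 says any. Section 6 distinguishes absolute from relative. Read literally, a relative one (raised resting heart rate or blood pressure) is enough for drop-out. The two sections need to be reconciled.

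**4. Does the SAP's 20% allowance cover the loss?** With the values as entered in SAP Section 2: 1.96 × √(2 × 0.553 × 0.447) = 1.378; 0.80 × √(0.653 × 0.347 + 0.453 × 0.547) = 0.551; (1.929 / 0.20)² = 93.0. That gives 93 per group and 186 in total; 186 + 37 = 223, as the SAP states. The allowance replaces lost numbers. It does not correct selective loss.

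**5. How large could the effect be?** The documents give no rate of new contraindications, so this is illustration only. Assumptions: two groups; 0.653 (vaccinated) and 0.453 (unvaccinated) are good-outcome proportions, although the SAP does not name the outcome; only poor-outcome subjects drop out, a share d of them. Then:

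observed proportion = p / [p + (1 − p)(1 − d)]

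Example with d = 0.10 vaccinated and 0.20 unvaccinated: 0.653 / (0.653 + 0.347 × 0.90) = 0.676; 0.453 / (0.453 + 0.547 × 0.80) = 0.509.

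| d, vaccinated | d, unvaccinated | Observed proportions | Difference (true 0.20) |
|---|---|---|---|
| 0.05 | 0.05 | 0.665, 0.466 | 0.199 |
| 0.20 | 0.20 | 0.702, 0.509 | 0.193 |
| 0.05 | 0.10 | 0.665, 0.479 | 0.185 |
| 0.10 | 0.20 | 0.676, 0.509 | 0.168 |
| 0.05 | 0.20 | 0.665, 0.509 | 0.156 |
| 0.20 | 0.05 | 0.702, 0.466 | 0.236 |

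(Differences are taken before rounding.) Equal drop-out inflates both proportions but leaves the contrast almost unchanged. Unequal drop-out shrinks or enlarges it, depending on which group loses more. With no true difference (0.453 in both), 0.05 against 0.20 gives 0.466 − 0.509 = −0.043.

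Total loss across the table runs from (0.347 × 0.05 + 0.547 × 0.05) / 2 = 2.2% to (0.347 × 0.20 + 0.547 × 0.20) / 2 = 8.9%, all inside the 20% allowance. Staying within the allowance would therefore not show that the loss was harmless.

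**The case against.** The strongest reply is that the rule is softer than a literal reading and its effect may be small. Section 9 says subjects may be discontinued and calls its list possible reasons. Section 10 asks that withdrawal be avoided where reasonably possible. Completing the CRF to the last visit is a minimum and does not forbid later questionnaires. Data already collected are kept, so only later visits are at risk. Some cases may in effect be late screening failures, because heart rate and blood pressure are first mentioned as measured at the 6MWT. All of this stands. It limits the size of the problem, but nothing in the text tells a site to continue the questionnaires.

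A reader might infer several stronger points that the documents do not support:
- **That the sickest subjects, or those too unwell to walk, are removed because their outcomes are bad.** Inability to walk is not among the contraindications in Section 6. Intolerable dyspnoea is listed there as a reason to stop a test in progress. A breathless subject with poor quality of life could stay, while one with raised blood pressure and good quality of life could leave.
- **That deaths belong to the same loss.** Quality of life cannot be collected after death. The issue there is that deaths count as drop-outs with no stated handling.
- **That SGRQ and SF-36 are completed online.** Section 5.4 ties online completion to the screening questionnaire. It is plausible for the other two but not stated. The point needs only that no walking is required.
- **That power falls from 0.82 to 0.61.** This extreme case takes 0.653 as the poor-outcome proportion and drops 15% against 5% of subjects, all with poor outcomes, from 100 per group: (0.653 − 0.15) / 0.85 = 0.592; (0.453 − 0.05) / 0.95 = 0.424; difference 0.168. But 100 per group is already 250 less 20%, halved, so attrition is counted twice; from 125 per group the power is 0.71. Part of the fall is smaller numbers alone: an unbiased 0.20 with 85 and 95 subjects has power 0.77. At 3% against 1% dropped from 100 per group, the difference is 0.195 and the power 0.79. The design also has four groups, not two.

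**Conclusion.** The point holds as a fault of wording with a real consequence. A rule about a secondary test can end collection of primary quality-of-life data that could still be obtained, and nothing in the readable protocol or SAP restores them. Confidence in that reading is high.

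That the loss is selective is plausible but not shown; it rests on the listed conditions being related to health status. The size and direction of any bias in the vaccination contrast are unknown and could be small. The scenarios show only that bias in the contrast requires unequal drop-out and can go either way, while the within-group description can be inflated even when drop-out is equal. The change is worth making because it is cheap and the data cannot be recovered later.

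**What to change.** - **Section 9, item 2:** separate not performing the 6MWT from leaving the study. Subjects who cannot do the 6MWT and have not withdrawn consent continue SGRQ, SF-36 and the symptom questionnaires at 3 and 6 months. Record the missing 6MWT and its reason. Whether the test is performed remains a clinical decision.
- **Section 10:** state that CRF completion continues for these subjects, and complete the sentence on follow-up.
- **Sections 6 and 9:** reconcile the wording on any contraindication with the absolute/relative distinction.
- **Separate point on deaths:** report deaths by vaccination group instead of counting them only as drop-outs, and state in the SAP how they and missing questionnaires are handled.

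Cost: amended wording and a few more questionnaires from subjects who would otherwise have left. If SGRQ and SF-36 are not in fact completed remotely, the plan should say how they will be obtained from subjects who do not attend for the walk test.

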## **10. Handling of Participant Withdrawals or Termination**

Although subjects may withdraw from the study at any time and for any reason, (or may be withdrawn at the investigator's discretion), subject withdrawal should be avoided as much as reasonably possible. In any case, appropriate follow-up for withdrawals or termination. Subjects who are discontinued are not to be replaced. For subjects considered discontinued, the CRF must be completed up to the last visit performed.

## **11. Privacy and Confidentiality**

Paper records for this study will be maintained in locked cabinets in Internal Medicine Departments. Electronic records for this study will be maintained on password-protected computers on which security is protected by firewalls. Files containing patient data will be stored in a locked office and/or on a password-protected

computer with access granted only to those individuals listed on the research team. Presentation of research results in scientific meetings/conferences and publications in scientific journals will not include participants' identities.

## STATISTICAL ANALYSIS PLAN

### 1. Randomization

Subjects who meet all inclusion and exclusion criteria will be allocated into four groups; Never been vaccinated, received 1st dose, received 2nd dose, and received 3rd dose of vaccination. Subject allocation will be carried out through block randomization and known only by the pharmacist, and confidentiality is maintained so that subjects, doctors/nurses, researchers, and data analysers do not know the allocation of each subject.

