## PROTOCOL SYNOPSIS

Title	COVID-19 Vaccination Status and The Characteristics and Clinical Outcomes of Long COVID-19 Patients in [name] General Hospital
Sponsor	University of Indonesia
Study Rationale	
Long COVID is the persistence or emergence of symptoms for more than four weeks beyond the acute phase of Severe Acute Respiratory Syndrome – Coronavirus-2 (SARS-CoV-2) infection. Various multi-organ complications after COVID-19 infection include respiratory, cardiovascular, gastrointestinal, hepatobiliary, metabolic, and neuropsychiatric disorders. The symptoms and characteristics of Long COVID vary in each country.
 
Vaccination against SARS-CoV-2 has been documented to increase the clinical resolution of Long COVID. However, in Indonesia, current full-dose vaccination coverage has merely reached 15.6% of the national vaccination target. This condition can be predictably associated with a longer duration and higher severity of symptoms in Long COVID patients.
 
This study's point of view is to describe the incidence and the characteristic of long COVID in patients and the impact of COVID-19 vaccination on the clinical outcome of long COVID. In addition, this study is expected to reinforce the recommendation for the COVID-19 vaccine implementation in Indonesia. The result of this study can be applied in clinical practice to ascertain the benefits of SARS-CoV-2 vaccination to improve clinical outcomes and quality of life; and reduce symptoms, duration, and frequency of long COVID.

Study Objectives	
Primary
 
 
• To provide an overview of the symptoms and characteristics of Long COVID patients at [name] General Hospital.
 
• To determine whether vaccination against SARS-CoV-2 could improve clinical outcomes and quality of life of Long COVID patients at [name] General Hospital.
 
 
Secondary
 
 
• To determine whether vaccination against SARS-CoV-2 could increase functional exercise capacity of Long COVID patients.
 
• To determine whether vaccination against SARS-CoV-2 could reduce symptoms, duration, and frequency of Long COVID.
 

Study Design	Prospective cohort study

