Subject Population Key criteria for Inclusion and Exclusion:	
Inclusion Criteria
 
 
1. Adult patients, aged <math>\geq 18</math> years old with a history of laboratory-confirmed SARS-CoV-2 infection via a positive molecular (RT-PCR) or antigen (lateral flow assay) test, receiving outpatient/inpatient care from [name] General Hospital, any time prior to enrollment in this study.
 
2. Patients with/without comorbidities.
 
3. Willing to fill-out online Long COVID symptoms follow-up questionnaire.
 
4. Willing and able to comply with the trial protocol, 6 Minutes Walking Test (re-visits and physical testing).
 
 
Exclusion Criteria
 
 
1. Patients with no registered medical record number (MRN) at [name] General Hospital.
 
2. Refusal to participate in the study or to sign the informed consent form.
 
3. Contraindicated to perform the 6 Minutes Walking Test.
 
4. Patients with no access to a smartphone or computer (desktop, laptop, or tablet) to fill out the online screening questionnaire.
 
5. Patients who died during or before enrollment in the study.
 

Number of Subjects	
A total of 250 subjects are divided into 4 groups according to SARS-CoV-2 vaccination status:
 
 
• Never been vaccinated.
 
• Received 1st dose of vaccination.
 
• Received 2nd dose of vaccination.
 
• Received 3rd dose of vaccination.
 

Study Location	[name] General Hospital, Central Jakarta, Jakarta, Indonesia
Study Duration	Each subject's participation will last for 6 months. The estimated duration for the main protocol is approximately 1 year.
Study Phases	
Screening Screening for eligibility and obtaining consent.
 
Study Examination Online questionnaire filling, 6-Minute Walking Test (6MWT)
 
Follow-up Follow-up examination 3 and 6 months after baseline.

Safety Evaluations	
Adverse events will be monitored and collected by the study team from the point of signed consent until the adverse event(s) are resolved and subjects are stabilized. Adverse events will be managed according to the 6MWT guidelines of the American Thoracic Society (ATS).

---

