#### 4. Study Duration and Timeline

No.	Activity	Description	Timeline
1.	Preparation and approval of the proposal	Create and revise proposals and activity plans according to the discussions of the research team and collaborators	September 2021
2.	Ethics approval	Submit an ethical review to the health research ethics committee of FKUI-RSCM	October 2021
3.	Data collection phase I	Collecting data from the patient's medical record	November 2021 – December 2021
4.	Data collection phase II	Collecting data from the online questionnaire, 6MWT, and follow-up	March 2022 – November 2022
5.	Data analysis	Data tidying, completing, and analysis	December 2022 – February 2023
6.	Report writing	Writing the final report on the results of the research	March 2023
7.	Publication	Publication of research results	April 2023

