#### 5. Methods

##### 5.1. Study Design

This is a prospective cohort, cross-sectional study involving two hundred and fifty (250) subjects of post-acute COVID-19 patients, receiving outpatient/inpatient care from [name] General Hospital during the acute phase of the infection, any time prior to enrollment in this study.

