## 5.2. Study Population and Selection Criteria

All participants will be required to sign a written informed consent, be willing and able to comply with all study requirements, and should meet the following criteria:

1. Adult patients, aged  $\geq 18$  years old with a history of laboratory-confirmed SARS-CoV-2 infection via a positive molecular (RT-PCR) or antigen (lateral flow assay) test, receiving outpatient/inpatient care from [name] General Hospital, any time prior to enrollment in this study
2. Patients with/without comorbidities
3. Willing to fill-out online Long COVID symptoms follow-up questionnaire
4. Willing and able to comply with trial protocol (re-visits and physical testing)

Subjects will be **excluded** from the study based on the following criteria:

1. Patients with no registered medical record number (MRN) at [name] General Hospital
2. Refusal to participate in the study or to sign the informed consent form
3. Any contraindications for 6 Minute Walking Test according to the guidelines of the American Thoracic Society (ATS)
4. Patients with no access to a smartphone or computer (desktop, laptop, or tablet) to fill out the online screening questionnaire
5. Patients who died during or before enrollment in the study

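### Vaccine doses are not ordered against infection or recovery, so comparisons of recalled Long COVID symptoms, duration and frequency cannot be read as vaccine effects

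*Combined protocol and SAP*

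**What the plan says.** **Exposure.** The Synopsis (Number of Subjects) says "A total of 250 subjects are divided into 4 groups according to SARS-CoV-2 vaccination status": none, one, two or three doses. SAP section 1 repeats this: "Subjects who meet all inclusion and exclusion criteria will be allocated into four groups". The natural reading is doses received by enrolment. Neither place mentions the date of infection, symptom onset or recovery.

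**Infection.** Section 5.1 takes patients treated at the hospital "during the acute phase of the infection, any time prior to enrollment in this study". The criteria in section 5.2 set no minimum or maximum interval and do not require current symptoms, so people who have already recovered are eligible.

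**Outcomes and dates.** Under section 5.4, Long COVID symptoms, "severity, and duration are collected through online screening questionnaire". The same questionnaire records vaccination "status (including the amount, type, and when the vaccine was received". SGRQ, SF-36 and the 6-minute walk are measured at baseline, 3 and 6 months. Section 5.2 also mentions a follow-up questionnaire: "Willing to fill-out online Long COVID symptoms follow-up questionnaire".

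**Analysis.** The Synopsis and SAP section 3.2.2 name a chi-square or Fisher test at the 0.05 level. No rule uses the dose dates, and none covers doses received during follow-up.

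**Aim.** Section 2.2 asks whether vaccination reduces symptoms, duration and frequency of Long COVID. The rationale is "Vaccination against SARS-CoV-2 has been documented to increase the clinical resolution of Long COVID".

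**The concern.** The objective is causal and the rationale works through resolution, so a dose can act only on symptoms that are still present when it is given. Grouping by dose count at enrolment makes two errors for an illness that lies wholly or partly before enrolment:

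- A person who recovered and was vaccinated afterwards counts as vaccinated with a short illness, although that dose could not have shortened it.
- A person vaccinated while symptomatic has the whole illness counted as vaccinated, including the months before the dose.

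The consequence depends on why people were vaccinated when they were. If timing is unrelated to symptoms, the test keeps its level but a real effect is diluted. If symptomatic people defer vaccination, a useless vaccine looks beneficial. If they seek it, the vaccine looks harmful. The documents do not say which applies. At stake are the recalled part of the secondary objective in section 2.2 and any clinical outcome under the primary objective in section 2.1 that is taken from recall.

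The timeline in section 4 leaves room for this. Phase I ("Collecting data from the patient's medical record") runs November to December 2021 and questionnaires start in March 2022. If the phase I patients are the ones enrolled, each had at least two months (January and February 2022) between infection and questionnaire in which a later dose would still count.

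**Working it through.** **The plan's own figure.** SAP section 2 computes n = [(1.96√(2 × 0.553 × 0.447) + 0.80√(0.653 × 0.347 + 0.453 × 0.547)) / 0.20]² = 93.04, which matches the stated 93 per group. No term depends on dose timing, so the figure neither supports nor refutes this point.

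**Inputs from the documents.** 250 subjects; Long COVID prevalence 0.40 (SAP section 2), hence 250 × 0.40 = 100 Long COVID patients; level 0.05.

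**Assumptions, not in the documents.** Vaccine rollout starts 14 months before enrolment. The first-dose rate is 0.1 per month, multiplied by k while symptomatic. With k = 1 the share vaccinated at enrolment is 1 − exp(−0.1 × 14) = 75%. Infection is uniform over a window before enrolment. In the main duration shape, 40% have symptoms for 1 month plus an exponential time at 0.1 per month, and the rest recover within a month. Results are by simulation.

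**1. Real effect, timing unrelated to symptoms (k = 1).** A dose doubles the resolution rate while symptomatic. The reading is a rate ratio, in essence (resolutions ÷ symptomatic months in the ever vaccinated) ÷ (the same in the never vaccinated), grouped by status at enrolment.

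| Infection before enrolment | Vaccinated Long COVID patients whose first dose came after symptoms ended | A true 2.0 reads |
|---|---|---|
| 2–6 months | 1.7% | about 1.9 |
| 2–12 months | 7.7% | about 1.8 |
| 6–12 months | 12% | 1.7–1.8 |
| 6–24 months | 38% | 1.4 |

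With dated doses in a time-dependent Cox model, the reading is 2.00 in both the 6–12 and 6–24 month windows.

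**2. Useless vaccine, ever versus never vaccinated, all 250, duration over 1 or 3 months.** With k = 1, about 5% of trials are significant, as they should be. With k = 0.5 (apparent benefit) or k = 2 (apparent harm):

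| Infection before enrolment | Significant |
|---|---|
| 2–6 months | about 12–20% |
| 2–12 months | about 23–40% |
| 6–12 or 6–24 months | about 34–56% |

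With k between 0.8 and 1.25 the figure is about 6–10%. Duration shape matters too. Holding prevalence at 40%, infection at least 6 months back and k = 0.5 or 2, an intermediate shape (Weibull, shape 0.5) gives 13–26% over 1 month and 19–32% over 3 months. If nearly all symptoms end within 3 months, the figures are 6–9% and 5–8%.

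**3. The obvious shortcut.** Recode people dosed after recovery as unvaccinated. The vaccinated group then contains only people who were still symptomatic when dosed, or were dosed before infection, while early recoverers move to the comparison group. This is immortal-time bias: a true 2.0 reads about 1.1 (6–12 months) or 0.65 (6–24 months).

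**4. The proposed analyses under a useless vaccine, k from 0.5 to 2.** Time-dependent Cox rejects in 4.2–6.0% of trials, the landmark analysis in 4.2–6.1%, and pre-infection doses with the outcome read at 1 month since infection in 4.9–5.2% (two groups).

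**The case against.** **Size.** The size is driven by an infection window that the documents do not give. If most infections were 2–6 months before enrolment, few doses fall after recovery and the dilution is slight. Changing rollout (10 to 18 months) and dose rate (0.05 to 0.2 per month) under the long-lasting shape, with infection at least 6 months back, moves the false-positive rate over 17–77% at k = 0.5 and 0.1–80% at k = 2. This stands: the figures show what can happen and do not predict it.

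**Scope.** Quality of life and exercise capacity rest on instruments measured at baseline, 3 and 6 months. Some symptoms are current at enrolment or collected in follow-up. This also stands. A reader might infer that every vaccine comparison in the study is invalid, but the documents support that only for recalled outcomes.

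**Missing figures.** The figure under SAP section 3.2 and the flow diagram in SAP section 4 are not shown. Either could hold a timing rule, which limits confidence to medium.

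**Data.** Section 5.4 lists dose dates, infection history and symptom duration, but not symptom onset or end dates. The remedy for duration is therefore not free of new data.

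**Randomization.** SAP section 1 describes block randomization with concealed allocation, which a reader might take to place exposure before outcome. It conflicts with a cohort grouped by existing vaccination status (Synopsis), so it cannot be relied on.

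**Conclusion.** The point holds for recalled outcomes. The visible text defines exposure by dose count only. Applied as written to symptoms, duration and frequency recalled at screening, the planned test misplaces both pre-dose symptomatic time and post-recovery doses. Neither a positive nor a null result there can be read as a vaccine effect. The 3- and 6-month SGRQ, SF-36 and 6-minute walk results are less exposed, although doses received during follow-up have no rule.

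Direction and size are unknown. Under the stated assumptions, a true resolution rate ratio of 2.0 reads 1.9 to 1.4 when timing is unrelated to symptoms. A useless vaccine is significant in about 12–56% of trials when symptomatic people are vaccinated at half or twice the usual rate and symptoms last long. Inflation is small if rates differ little or symptoms end quickly.

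Two stronger inferences are not supported. One is that the plan overstates vaccine benefit: dilution or apparent harm is equally compatible with the text. The other is that the only fault is crediting doses given after recovery: correcting that alone makes the bias worse.

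**What to change.** Amend SAP sections 1 and 3.2.2:

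1. **Recalled duration or resolution.** Treat each dose after infection as a time-dependent exposure from infection or symptom onset (Cox model, censored at the questionnaire), or use a landmark analysis among those still symptomatic. State that people dosed after recovery are not to be simply reclassified as unvaccinated. With about 100 Long COVID patients and a true ratio of 2.0, the time-dependent model has 77% or 83% power (infection 6–12 or 6–24 months back). A 3-month landmark with a binary 6-month outcome has only 30–31%.
2. **Occurrence or frequency of Long COVID.** Count only doses before the index infection and read the outcome at a fixed time since infection, as an analysis separate from resolution.
3. **3- and 6-month outcomes.** Fix the dose count at enrolment, ask about new doses at the existing visits, and add a sensitivity analysis that updates or censors at a new dose.

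Report recalled and prospectively collected symptoms separately. Reconcile the block-randomization text with the cohort design.

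**Condition.** Item 1 needs duration as a continuous time or symptom onset and end dates. The questionnaire should record these.

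**Cost.** SAP wording, modest analysis work and a few questionnaire items. Dose-by-timing cells will be small and need pooling: in the simulation, three doses before infection covered only about 2–5 of 250 subjects. Recently infected subjects drop out of fixed-time outcomes. These changes correct time order only; confounding needs its own adjustment.
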